4.4 Sample size calculation

Based on the main objective, it is expected that FDG-PET/CT can reduce unjust treatment from ~73.1% (=136/186 benign lesions >10mm) to ~40.3% (=75/186 false-positive and false-negative lesions >10mm, §1.3, p19). Using G*Power version 3.1.9.2. (and validated using JMP from SAS version 9.0.1, STATA version 12.0SE and PASS version 2011), we computed using an α error probability of 0.025 (=0.05/2, Bonferroni correction for interim analysis) a power of 0.80 and an allocation ratio of N_A:N_B=2:1, we need to include at least 90 patients in total (one-tailed test) to establish this difference (60+30 patients in arm A and B respectively).

Since around 82.7% (=186/225, §1.3, p19) fulfil the size criterion, at least 111 patients (74+37 patients in arm A and B respectively) need to be included. Accounting for additional 15% data loss at the final end-point, 132 patients should be included (88+44 patients in arm A and B respectively) (Figure 2, p40).

This total number of patients could at best (assuming no data loss) discern a reduction of 26.6% unjust treatment in the whole population with an actual α error probability of 0.016 and a power of 0.80. This is based on a reduction from 74.2% (prevalence of benign disease in all 225 patients) to 47.6%. In the experimental arm (88 patients), where the number of false-negative PET is estimated to be ~1.3% (3/225), this number of patients should establish a false-negative rate of maximal 7.5% (actual α error probability of 0.0066 and a power of 0.80). All analyses will be performed according to the intention-to-treat principle, meaning that analysis is based on the initial study-arm allocation and not on the treatment eventually received (e.g. a FDG-PET/CT negative patient in the experimental arm does not refrain from surgery and therefore actually is treated according to the control study arm).

[figure not shown]

Figure 2: Relation between study size (N), study-arm size sizes (n₁ and n₂) and effect size. Empirical relation: N=16.33935*ES^{-1.86986}, R²=.999443). Expected ES=73.1%-40.3%=32.8%

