10.3 Univariate analysis

All comparisons will be made using the general requirements for relating research questions as stated in Table 6, p66.

Characteristics of (independent) study-arms will be compared using either t-tests ((log)normal) or Wilcoxon rank-sum tests for continuous variables (e.g. age, SUV, hospitalisation days, volumes of care used, questionnaire scores). For categorical data either Fisher exact tests or χ^2 tests will be used (e.g. sex, unbeneficial patient management).

With respect to the primary research question, fractions unbeneficial patient management therefore will be compared using Fisher exact tests or χ^2 tests.

Relations between variables will be univariately described by the parameters from Table 7, p66. These parameters are compared using the tests from Table 8, p67.

Scale:	Groups:	Dependency:	Group Size:	Distribution:	Test:
Continuous	1	n/a	n≥30	(Normal)	t-test
(and			n<30	Normal	_
categorical ordinal)				Not normal but transformable	Transform than t-test
				Not normal, not transformable	Sign test
	2	Independent	n≥30	(Normal)	t-test
	-	n<30		Normal, equal variances	
				Normal, non-equal variances, equal n's	-
				Normal, non-equal n's, transformable	Transform than t-test
				Normal, non-equal variances, non-equal n's, not transformable	Wilcoxon rank-sum tes (= Mann-Whitney U test
				Not normal, transformable	Transform than t-test
				Not normal, not transformable	Wilcoxon rank-sum tes (= Mann-Whitney U test
		Dependent	n≥30	(Normal)	Paired t-test
			n<30	Normal	_
				Not normal, transformable	_
				Not normal, not transformable	Wilcoxon signed ranks
	≥3	Independent	n/a	Normal, 1 factor	One-Way ANOVA
				Normal, ≥2 factors	Two-Way or othe ANOVA
	_		Not normal	Kruskal-Wallis for Factor (+Dunn's posthoo test)	
		Dependent	n/a	Normal	Repeaed Measures
				Not normal	Friedman ANOVA
Categorical (Nominal)	1		np≥5 and n(1- p)≥5		z-approximation
	2	Independent	Expected cell frequencies <5		Fisher's Exact Test
≥3	_		Expected cell frequencies ≥5		X ² or z-approximation
		Dependent			McNemar or ĸ
	≥3	Independent	Expected cell frequencies <5		Collapse categories fo X^2
			Expected cell		X ²
			frequencies ≥5		

Table 6: General Requirements for selection of Statistical tests used for univariate analysis (comparison)

Predicting each other	Parameter:
	Relative Risk
	Spearman's ρ squared
yes	Regression
no	Pearson's Correlation R squared (log)normal
	Spearman's p squared (not-normal)
	yes

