11.4 Benefits and risks assessment, group relatedness

The benefits for the individual patient is that he or she as a 2/3 probability to be included in the experimental arm in which only ~60-65% will be operated upon (instead of ~100% in the control study-arm, which is considered standard care). By lowering the amount of unnecessary invasive procedures also the number of complications and side effects are lowered.

As described elsewhere in detail (§13, p78), the risk for the individual patients are mainly based on delayed treatment for the indolent growing DTC in case of a false-negative PET-scan in the experimental study arm and the risks attached to the use of ionising radiation and of incidental PET findings.

The risks of consequences of delayed treatment for DTC are minimised by using a confirmatory US in the individual patient (§8.3.2, p52) and by performing interim- (§8.7, p58) and posthoc (§8.4.1, 56) analyses on the control study arm (in which both FDG-PET/CT and final histology is obtained).

The risk of ionising radiation (§15.6, p97) is minimised by several means: using (ultra) lowdose CT, minimising the scan range, thus minimising the amount if tissue exposed to (ultra) low-dose CT radiation and exclusion of minors that would both have increased effective dose per amount of FDG and suffer more detriment per unit of effective dose. By decreasing the scan range, the scan time is also limited, encouraging nuclear medicine departments to scan at a decreased speed (e.g. 4 min per bedposition or longer) by which means they can lower the administered FDG-dose.

The risks of additional (invasive) diagnostic procedures for incidental PET-findings is minimised by only scanning head, neck and thoracic inlet.

The burden to the patients consist of a single FDG-PET/CT (1.5h, in all patients, §8.3.1, p48), a single confirmatory US (0.5 h, in ~35-40% of the experimental arm or approximately ~25% of all patients included, §8.3.2, p52) and 4 times 6 questionnaires (120-160 min, in all patients, §8.3.3, p52). On average these 3 types of investigation therefore take in total 4-4.5 h per patient.

Travel expenses of included patients to and from the hospital will be compensated for the FDG-PET/CT and the confirmatory US (\in 0.19/km or comparable and possible additional costs for parking at the hospital, according to the locally set reimbursement rates and in consultation with the project leaders).

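### Table 6 sends two groups of 30 or more to a t-test with no variance condition; with 2:1 arms of different make-up the test should be named as Welch's

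*Protocol*

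**What the plan says.** Section 10.3 gives Table 6 ("General Requirements for selection of Statistical tests used for univariate analysis") general force: "All comparisons will be made using the general requirements for relating research questions as stated in Table 6". The accompanying text applies the choice between t-test and Wilcoxon to continuous outcomes ("e.g. age, SUV, hospitalisation days, volumes of care used, questionnaire scores").

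For two independent groups the table splits on size. At 30 or more the whole entry is "Independent n≥30 (Normal) t-test". Below 30 it looks at variances. The t-test is kept for "Normal, equal variances" and for unequal variances with equal group sizes. It gives way to Wilcoxon for "Normal, non-equal variances, non-equal n's, not transformable". No unequal-variance t-test is named anywhere.

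On arm sizes, section 4.4 states that "132 patients should be included (88+44 patients in arm A and B respectively"), and that 60 and 30 are to be analysed for nodules above 10 mm. On composition, section 11.4 describes an experimental arm "in which only ~60-65% will be operated upon (instead of ~100% in the control study-arm").

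**The concern.** The small-sample rows show that the authors knew the weak spot of the pooled t-test: unequal variances combined with unequal group sizes. Above 30 the condition disappears, as if sample size cured it. Sample size helps with non-normality. It does not help here: the pooled standard error weights the two variances in the wrong proportion, and the resulting error stays the same as both arms grow at a fixed 2:1 ratio.

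Both arms fall in the row without the condition, and their make-up differs by design. If the larger arm varies more, p-values are too large and intervals too wide. If the smaller arm varies more, the reverse holds. At stake are the secondary continuous comparisons: hospital days, sick leave, volumes of care and questionnaire scores.

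**Working it through.** **1. Arm sizes.** Exact power of the one-sided Fisher test at 60 and 30 patients, with rates 75/186 and 136/186 and alpha 0.025, is 0.801. This reproduces the stated 0.80. Inflation for 15% loss gives 111/0.85 = 131, or 132 as a multiple of three: 88 and 44.

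**2. Formula.** Let r be the variance in arm A divided by that in arm B, and k the pooled standard error divided by the true one:

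k = √{ [((nA−1)r + (nB−1)) / (N−2)] × (1/nA + 1/nB) / (r/nA + 1/nB) }

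The true two-sided size at nominal 5% is about 2 × [1 − Φ(k × 1.978)], where 1.978 is the t quantile on 130 degrees of freedom.

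**3. General behaviour at 88/44** (normal data, equal means, 40,000 simulated trials per row):

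| r | k | Pooled size | Welch size |
|---|---|---|---|
| 0.25 | 0.81 | 11.0% | 4.9% |
| 0.5 | 0.89 | 7.8% | 5.0% |
| 1 | 1.00 | 5.0% | 4.9% |
| 2 | 1.12 | 2.8% | 5.0% |
| 4 | 1.23 | 1.9% | 5.2% |

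At 60/30 the pooled figures are almost the same (11.0%, 8.1%, 4.8%, 2.9%, 1.7%). At 66/66 the pooled test stays at 5.0–5.2% for every r, so the unequal allocation is what exposes it.

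**4. Which r the design can produce.** Section 3 expects surgery to be cancelled in about 32 arm A patients, so the operated share is q = 56/88 = 0.636. Assume that operated patients have the same mean and coefficient of variation (CV) in both arms and that unoperated patients score 0. Then r = [q·CV² + q(1−q)] / CV².

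| CV among operated (assumed) | r | Size of pooled test (formula) |
|---|---|---|
| 0.25 | 4.34 | 1.4% |
| 0.5 | 1.56 | 3.3% |
| 0.8 | 1.00 | 4.8% |
| 1 | 0.87 | 5.3% |
| 2 | 0.69 | 6.3% |

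The direction reverses at CV = √0.636 ≈ 0.80. As CV grows without limit, r falls to q. At r = 0.636, k = 0.928 and the size is 6.6% by formula, 6.9% by simulation. With q = 0.60 the formula gives 6.9%. About 7% is therefore the ceiling under this mechanism.

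**5. A case from the protocol's own figures.** Unit costs are in section 1.4.1 and the pooled counts in section 15.4 (TP 55, FP 87, FN 3, TN 80; total 225).

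- PET-negative and unoperated: €488.
- Benign, operated: 4,419 + 1,080 = €5,499.
- Malignant, operated: 4,419 + 1,080 + 6,618 + 2,479 = €14,596.
- Arm A shares: 83/225, 87/225 and 55/225. Mean €5,874, SD €5,418.
- Arm B shares: 0, 167/225 and 58/225. SD = 9,097 × √(58/225 × 167/225) = €3,979.

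The SD ratio is 5,418/3,979 = 1.36, so r = 1.85 and k = 1.106. The simulated size is about 3% pooled and 5% Welch.

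This case gives every patient in a category the same cost. Adding a within-category SD s among operated patients gives r = (5,418² + (142/225)s²) / (3,979² + s²):

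| s (assumed) | SD ratio | Simulated pooled size |
|---|---|---|
| €2,000 | 1.27 | 3.4% |
| €4,000 | 1.11 | about 4.2% |
| €6,000 | 1.00 | 5.0% |

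**6. Price of switching.** With equal variances and a true difference of 0.5 SD at 88/44, simulated power is 76.7% pooled and 76.4% Welch.

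**The case against.** Table 6 says only t-test. Neither the pooled nor the Welch form is named, and such a choice can be left to an analysis plan that is not shown here. This stands in part: the pooled form is an inference. But leaving the t-test when variances and group sizes are both unequal has a purpose only for the pooled form. The protocol also does not leave the matter open; it fixes a selection rule with a condition on one side of the cut and none on the other.

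The text of section 10.3 chooses between t-test and Wilcoxon on (log)normality. Hospital days that pile up near zero in unoperated patients might therefore go to Wilcoxon. That is a fair reading, and it narrows the point to wherever a t-test is used. It does not remove it, because the bracketed normality entry at 30 or more reads equally well as an assumption.

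A reader might infer that arm A's variance is larger as a matter of fact. The documents do not show this: they give no standard deviations, and steps 4 and 5 show the excess shrinking to nothing as variation among operated patients grows, with step 4 going on to a reversal. A reader might also take the 11% row of step 3 as this trial's risk of a false claim. It needs arm B to have four times arm A's variance. If operated patients vary alike in both arms, the SD ratio cannot fall below about 0.80.

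The cost case also assigns completion surgery and radioiodine to every cancer, although section 1.1 exempts unifocal papillary microcarcinoma. It is an illustration, not an estimate.

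**Conclusion.** The point holds as a minor flaw in a stated rule. Under the pooled reading, the true size of a nominal 5% two-arm comparison lies between about 1.4% and 7% across plausible operated and unoperated mixtures. The likelier direction, if operated patients vary moderately, is conservative: a real difference in hospital days or care volumes becomes somewhat harder to show. The range assumes CVs from 0.25 upwards, unoperated patients at zero, and similar variation among operated patients in both arms. For questionnaire scores, where unoperated patients do not score zero, the documents support only that variances may differ.

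The primary endpoint is compared by Fisher or chi-square, and uncertainty in the cost-effectiveness ratio comes from the bootstrap or Fieller method. Neither is touched.

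**What to change.** In Table 6, for two independent groups of 30 or more, replace the bare t-test by Welch's unequal-variance t-test with its confidence interval, wherever a t-test is the chosen method. The rows below 30 do not govern the main two-arm comparisons and need not change for this purpose.

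The cost is one line of wording and, if variances turn out equal, about 0.3 percentage points of power in the example of step 6. No data collection, sample size or procedure changes.

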10.4 Multivariate analysis

Where appropriate, multivariate analysis will be performed to show the independent contributions of various factors to a single event or outcome. By this means, factors are explored contributing to FDG-PET/CT false negativity, FDG-PET/CT uptake (SUV), (overall and disease-free) free survival, etc. Multivariate modelling will be performed based on the characteristics of the individual data, candidate variables must show univariate significant association. Iterative forward (1 to many) and backward (many to 1) models will be evaluated based on thresholds for in- and exclusion. See Table 10, p68.

Scale of Independent:	Scale c Dependent:	of	Observations:	Confounding Independent:	Model:
Nominal	Nominal		Censored		Kaplan-Meier
			Not censored	Yes	Mantel-
					Haenszel
				No	Log-Linear
	Numerical		Censored		Cox
					Proportional
					Hazard
			Not censored		ANOVA
Nominal &	Nominal		2-values		Logistic
Numerical		dependent		Regression	
			(binary)		
			≥3 values		Classification
			dependent		methods
	Numerical		Censored		Cox
					Proportional
					Hazard
			Not censored	Yes	ANCOVA
				No	Multiple
					Regression

Table 10: Models for assessment of independency in multivariate modelling.

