2.2 Secondary Objectives

2.2.1 Secondary Objective 1: Treatment Outcome

- SO1a: To determine the difference in unbeneficial treatment between FDG-PET/CT driven and routine surgery in this population including thyroid lesions of all sizes (i.e. both ≤10 mm and >10mm).
- SO1b: To determine the effect of incorporation of FDG-PET/CT on the complication-ratio.
- SO1c: To determine the false-negative rate of FDG-PET/CT in this population (i.e. in how many patients with malignancy will watchful-waiting be performed) based on both 12-month and (retrospective) 5-year follow-up.
- SO1d: To determine the influence of lesion size, pathological classification and patient characteristics on the diagnostic accuracy (subgroup analysis) of FDG-PET/CT.
- SO1e: To determine whether incorporation of FDG-PET/CT of the head and neck leads to overdiagnosis in non-thyroidal incidental findings (whole-group analysis).
- SO1f: To determine the short-term overall and disease free survival in both study arms.
- SO1g: To determine which factors hamper implementation of this modality for this indication (structured interviews).
- SO1h: To determine the fraction of patients that cannot be reassured by a negative PETscan (experimental arm only) despite careful selection of patients (implementability).

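### The univariate screen and stepwise selection in section 10.4 cannot support a model of false-negative FDG-PET/CT on the roughly two events that the protocol expects

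*Protocol*

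**What the plan says.** Section 10.4 opens conditionally: "Where appropriate, multivariate analysis will be performed to show the independent contributions of various factors" to an outcome. It then states that "factors are explored contributing to FDG-PET/CT false negativity"; uptake (SUV) and survival are the other outcomes that it names. Entry to a model is by p-value: "candidate variables must show univariate significant association". Selection follows: "Iterative forward (1 to many) and backward (many to 1) models will be evaluated based on thresholds for in- and exclusion". Neither the screening level nor the selection thresholds are given. Table 10 assigns a two-valued outcome with mixed nominal and numerical predictors to logistic regression, and purely nominal predictors to Mantel-Haenszel or log-linear analysis. The section has no minimum event count, no cap on predictors and no method for sparse data.

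The event count follows from section 4.4: "132 patients should be included (88+44 patients in arm A and B respectively"), and "the number of false-negative PET is estimated to be ~1.3% (3/225"). The addendum to section 4.5 confirms that 132 were enrolled. Sections 8.4.1 and 8.7 accept a false-negative ratio of up to 5%. Section 8.3.4 also counts a non-avid borderline lesion (NIFTP, FT-UMP, WDT-UMP) as false negative.

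Secondary objective SO1d in section 2.2.1 is a separate item: "To determine the influence of lesion size, pathological classification and patient characteristics on the diagnostic accuracy (subgroup analysis) of FDG-PET/CT".

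**The concern.** Screening on univariate significance and then selecting stepwise needs enough events for a p-value to carry information about effect. With about two events, whether a grouped factor can pass depends mainly on how common its level is. A common factor would drop out without ever having been testable, and a rare one could enter on two coincident cases.

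The section presents its output as independent contributions. A reader could then conclude that Bethesda class or age group has no bearing on missed malignancy, or that sex or size class has, when the data could not show either.

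**Working it through.** **Inputs.** N = 132 and 3/225 (section 4.4). 83 PET-negative patients and 58 malignancies among 225 (section 1.3 and Appendix IV). Level fractions from Table 4: 0–10 mm 13%, >40 mm 13%, male 20%, Bethesda IV 33%, age <45 40%. Fisher's exact test where expected cell counts are below 5 (Table 6). The screening level is not stated; 0.05 two-sided is assumed.

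**The plan's own figures.** 3/225 = 1.33% of all patients and 3/83 = 3.6% of negative scans. Both agree with the protocol.

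**Expected events.**
- All patients: 132 × 3/225 = 1.76.
- Control arm, where surgery is planned whatever the scan shows: 44 × 3/225 = 0.59.
- At the accepted ceiling: 132 × 0.05 = 6.6.
- Binomial at 1.33%: P(0) = 0.17, P(1) = 0.30, P(2) = 0.27, P(3) = 0.16, P(≥5) = 0.03.
- Ten events at this rate would need 10/(3/225) = 750 patients.

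**Smallest attainable Fisher p.** It is reached when all k events lie in the smaller level, of size m. For k = 2 it equals m(m−1)/(132 × 131), with denominator 17,292. For example, m = 17 gives 272/17,292 = 0.016, and m = 53 gives 2,756/17,292 = 0.159.

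| Level (m of 132) | k = 1 | k = 2 | k = 3 |
|---|---|---|---|
| ≤10 mm or >40 mm (17) | 0.129 | 0.016 | 0.002 |
| Male (26) | 0.197 | 0.038 | 0.007 |
| Bethesda IV (44) | 0.333 | 0.109 | 0.035 |
| Age <45 (53) | 0.402 | 0.159 | 0.063 |

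With two events, a binary factor can reach p < 0.05 only if its smaller level holds at most 29 of 132 patients (29 × 28/17,292 = 0.047; 30 × 29/17,292 = 0.050, just above the limit). With one event, none of these levels can pass.

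**Does the denominator matter?** Very little. For two events and the levels in table order:
- about 49 PET-negatives (132 × 83/225): 0.013, 0.038, 0.10, 0.16;
- about 34 malignancies (132 × 58/225): 0.011, 0.037, 0.10, 0.16.

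**Does the assumed level matter?** At a screening level of 0.10, Bethesda IV and age group still cannot pass on two events. At 0.20 both could.

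**Power for the levels that can pass.** Two events, relative risk 3, both events needed in the level:
- 13% level: (3 × 17/(3 × 17 + 115))² = 0.307² = 0.09.
- Male: (3 × 26/(3 × 26 + 106))² = 0.424² = 0.18.

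With seven events every level in the table can pass, but power at relative risk 3 is still only 0.27 to 0.42.

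**Separation.** If both events lie in one level, the other level has none. The odds ratio ad/(bc) then has c = 0, so maximum likelihood logistic regression has no finite estimate. The same zero makes the Mantel-Haenszel denominator zero and leaves an empty cell in the log-linear table.

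**The case against.** The strongest reply is that section 10.4 is already cautious. It says factors are explored, and only where modelling is appropriate. That stands against any claim that the section presents confirmatory models. It does not settle the matter, because the section gives no criterion for when to refrain, and it names false negativity first among its outcomes.

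The count is also uncertain. It could exceed 1.76 because borderline non-avid lesions count as false negative, and it could fall short because unoperated patients in the experimental arm may have no histology. At 1.33% there is about a 26% chance of three or more events, and with three Bethesda IV can pass. This stands, and it limits the exact p-values to a count of about two.

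A reader might infer more than the protocol supports:
- **That the entry rule governs the SO1d subgroup tests.** The rule concerns candidates for the multivariable models, and no text applies it to SO1d. The specificity part of SO1d rests on about 132 × 167/225 = 98 benign nodules, which the two-event argument does not reach.
- **That age or size can never be selected.** Section 10.1 lists age as continuous, and Table 6 treats ordinal categories with continuous data. A rank-sum test of 2 against 130 can reach 2/8,646 = 0.0002, and power for a 2 SD shift is about 0.7 to 0.8. The exclusion holds for two-level groupings only.
- **That each screening test is inflated.** With two events the null rejection rate is 0.016 for a 13% level and 0.038 for male sex. The weakness is low power, with selection governed by how common a level is.
- **That an error rate can be put on a family of subgroup tests.** The protocol fixes neither the family nor the correlation.
- **That these models decide who is left unoperated.** No passage uses them so.

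**Conclusion.** The point holds for the false-negativity model in section 10.4. On the protocol's own ratio about 1.8 events are expected in 132 patients, and no multivariable model with data-driven selection can be supported on that. At two events and a screening level of 0.05 (assumed), grouped factors can enter only if their level is at most about 22% of patients, so Bethesda class and age group at the Table 4 fractions are excluded in advance. At the 5% ceiling that exclusion disappears, but about seven events still give weak power and do not support stepwise selection among several factors.

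The primary endpoint, the sample size and the false-negative stopping rules are unaffected. This is a correction to a secondary, exploratory analysis, and worth making because the protocol fixes an unsuitable method instead of leaving the choice open.

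**What to change.** In section 10.4, for false negativity only:

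- Remove the univariate entry rule and the forward and backward selection.
- List each false-negative case, and give Clopper-Pearson intervals by ultrasound size class. Table 5 already names that interval.
- If a model is fitted at all, allow at most one pre-specified predictor, with Firth-penalised or exact logistic regression. Nodule size is the natural choice, since section 8.2.2 names it as a main determinant of sensitivity.
- Describe this analysis, and the false-negative part of SO1d in section 2.2.1, as exploratory.

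The change needs no new data, only protocol wording and slightly different analysis code. The downside is fewer independent predictors to report. The models for uptake and survival are outside this point, and no particular covariate set is asked for there.
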